4.8.7. Prior and Concomitant Medications

Prior and Concomitant medications will be coded using the WHO Drug dictionary. Frequencies and percentages will be presented for each treatment group and overall by the first level anatomical main (ATC 1) group and preferred name.

Prior medications are those the subject used prior to the first day of treatment.

All medications administered between the date of the first dose of study drug and the date of the last dose of study drug, inclusive, (i.e., all medications starting or ongoing during the time interval) are concomitant. A medication taken prior to Study Day 1 and continuing post Study Day 1 will be considered both prior and concomitant.

Concomitant medications tables will be presented for the following periods: Day 1 to Month 6 (treatment period) and Month 6 to Month 6 FU (follow-up period) as defined in section 4.2.12.

The use of prior and concomitant medications will be included in a by-subject data listing.

Prior interventional surgeries/procedures for endometriosis/endometriosis symptoms will also be summarized.

The use of Prior interventional surgeries/procedures for endometriosis/endometriosis symptoms will be included in a by-subject data listing.

4.8.8. Transvaginal Ultrasound (TVUS)

TVUS is performed at Screening, Month 3, Month 6, Month 3 and Month 6 of the follow-up period.

Actual values and changes from baseline will be summarized by treatment group and overall for uterine length, width, and depth in mm and corresponding uterine volume in cm³, endometrium thickness in mm.

The number and percentage of subjects with ovarian endometrioma with a diameter of 7 cm or greater, and presence of any uterine, left or right ovarian abnormality overtime will be presented by treatment group and overall.

All TVUS data for each subject will be provided in data listings.

4.8.9. Other Examinations

4.8.9.1. Endometrial biopsy

At least two endometrial biopsies for histological assessment must be obtained for each subject:

- One at screening (unless an endometrial biopsy was performed within the past 6 months prior to screening visit, which shows no endometrial atypical hyperplasia or adenocarcinoma and for which slides are available for current study assessment through retrospective central laboratory reading.

Sponsor:	ObsEva		
Protocol:	18-OBE2109-002		
Document Version No.:	1.0	Document Date:	18-MAY-2021

If more than one biopsy is done for screening, the last one before the first IMP administration will be analyzed.

- One at Month 6 if endometrial thickness in TVUS is > 5 mm
- One at Month 1 FU, 2 FU, 3 FU, 4 FU, 5 FU or 6 FU if not obtained at Month 6 or if the preceding biopsy diagnosis is different than "benign endometrium"

On biopsies with a primary diagnostic 1 either "hyperplasia" or "Malignant Endometrial Neoplasm", a second read should be done at other visit than screening. For hyperplasia diagnostic, in case of multiple readings of the same sample, the most severe diagnostics will be selected for the statistical analysis, considering the following order, from less severe to more severe: simple without atypia hyperplasia < simple with atypia hyperplasia < complex without atypia hyperplasia < complex with atypia hyperplasia. For Malignant Endometrial Neoplasm, we assume that there will be no difference on diagnostic between the readings.

Biopsies with a primary diagnostic 1 "Benign Endometrium" will be analyzed in the classification "Benign Endometrium without Hyperplasia or Atypia".

A summary at each time point will be performed (number and percentage of subjects with normal, abnormal, not assessable).

Biopsy assessment will be summarized by classification (primary diagnosis 1) and primary diagnoses (diagnoses 2, 3 and 4) at each visit. Subjects will be counted only once for classification (primary diagnosis 1 and a subject could be in several diagnoses (e.g. if for example diagnoses 2 and 3 are fulfilled).

Possible results by classification (primary diagnosis 1) and primary diagnoses (diagnoses 2, 3 and 4) are:

- Benign Endometrium without Hyperplasia or Atypia: Proliferative, Atrophic, Metaplastic Changes, Secretory, Indeterminate, Inactive, Polyp, Endometritis, Menstrual phase, Other
- Hyperplasia: Simple with Atypia, Simple without Atypia, Complex with Atypia, Complex without Atypia
- Malignant Endometrial Neoplasm: Carcinoma, Sarcoma, Other Malignant.

Endometrial biopsy results, including multiple readings, will be reported in listings.

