#### 10.4.5 Endometrial biopsies

At least two endometrial biopsies for histological assessment will have to be obtained for each subject:

- One at screening (unless an endometrial biopsy was performed within the past 6 months of the screening visit, which shows no endometrial hyperplasia of any type or adenocarcinoma and for which slides are available for current study assessment through retrospective central laboratory reading).
- One at Month 6 if endometrium thickness on TVUS is  $> 5$  mm (see Figure 3)
- One at Month 1 FU, 2 FU, 3 FU, 4 FU, 5 FU or 6 FU if not obtained at Month 6 or if the preceding biopsy diagnosis is different than “benign endometrium” but is not “malignant” or not “hyperplasia”(see Figure 4)

The endometrial biopsies will be analyzed by a central laboratory blinded to treatment group. Endometrial biopsies of hyperplasia of any type will be submitted for assessment by three independent expert pathologists who are blinded to the treatment and to one another’s assessment.

[figure not shown]

Figure 3 : Biopsy process for Month 6 study visit

[figure not shown]

Figure 4 : Biopsy process for the follow-up period visits

Screening endometrial biopsy should be performed at least 7 days after the first day of menstruation and sent for central assessment. If no tissue is available, the biopsy should be repeated as soon as possible in the following days. In case of multiple (at least two including the initial one) and unsuccessful attempts to get sufficient endometrial tissue, the subject is allowed to be randomized without any screening endometrial biopsy under the following conditions:

- a. The investigator confirms and documents in source that the subject has no signs of suspected endometrium malignancy (e.g. abnormal bleeding profile).
- b. The investigator and subject agree that at end of treatment all necessary actions will be taken to get a sufficient endometrium sample (e.g. short anaesthesia, if necessary). However, it should be noted that for subjects who discontinue the study and complete less than 3 months of treatment an end-of-study biopsy is not required.
- c. The medical monitor of the study approves the inclusion of the subject.

If there is a subsequent clinically significant finding in the biopsy, the subject will be withdrawn immediately

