- Table 14.4.9.2 ECG Findings up to Month 6 Follow-up – Safety Analysis Set
- Table 14.4.10.1 Gynecological Examination Findings by Visit from Day 1 to Month 6 Follow-up– Safety Analysis Set
- Table 14.4.11.2 Breast Examination Findings by Visit up to Month 6 Follow-up – Safety Analysis Set
- Table 14.4.12.1 Endometrial Biopsy Findings by up to Month 6 Follow-up– Safety Analysis Set
- Table 14.4.12.2 Endometrial Biopsy Diagnosis by Classification and Primary Diagnosis up to Month 6 Follow-up – Safety Analysis Set
- Table 14.4.13.1 Prior Medications – Safety Analysis Set
- Table 14.4.13.2 Prior Interventional Surgeries/Procedures for Endometriosis/ Endometriosis Symptoms – Safety Analysis Set
- Table 14.4.14.1 Concomitant Medications up to Month 6– Safety Analysis Set
- Table 14.4.14.2 Concomitant Medications from Month 6 to Month 6 FU – Follow-up Safety Analysis Set
- Table 14.4.15.1 Transvaginal Ultrasound: Uterus Length, Width, Depth, uterine Volume and Thickness up to Month 6 Follow-up – Safety Analysis Set
- Table 14.4.15.2 Transvaginal Ultrasound: Ovaries assessment up to Month 6 Follow-up – Safety Analysis Set

Sponsor:	ObsEva		
Protocol:	18-OBE2109-002		
Document Version No.:	1.0	Document Date:	18-MAY-2021

- Table 14.4.16.1 Suicide-related Treatment Emergent Events (C-SSRS) up to Month 6 – Safety Analysis Set
- Table 14.4.16.2 Suicide-related Events (C-SSRS) from Month 1 FU to Month 6 FU – Follow-up Safety Analysis Set

Post-text Listings

- Listing 16.1.7 Randomization scheme and codes (patient identification and treatment) - Randomized Set
- Listing 16.2.1.1 Subject Disposition and Study Termination Information – Part A - Randomized Set
- Listing 16.2.1.2 Subject Disposition and Study Termination Information – Part B - Randomized Set
- Listing 16.2.2.1 Inclusion Criteria – Screened Set
- Listing 16.2.2.2 Exclusion Criteria – Screened Set
- Listing 16.2.2.3 Protocol Deviations - Randomized Set
- Listing 16.2.3.1 Analysis Sets - Randomized Set
- Listing 16.2.3.2 Subjects with actual treatment not corresponding to any of the planned treatment groups - Safety Analysis Set
- Listing 16.2.4.1 Demographic and Baseline Information – Randomized Set
- Listing 16.2.4.2 Menstrual Cycle – Randomized Set
- Listing 16.2.4.3 Biberoglu & Behrman at Screening – Randomized Set
- Listing 16.2.4.4 Pelvic Pain Scores and Analgesic Use at Baseline – Randomized Set
- Listing 16.2.4.5 Endometriosis History – Randomized Set

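### Minor: choosing one "most severe" reading per biopsy can leave a recorded atypia finding out of the subtype rows of the endometrial safety table

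*SAP*

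**What the plan says.** SAP 4.8.9.1 sets the selection rule for hyperplasia: "in case of multiple readings of the same sample, the most severe diagnostics will be selected for the statistical analysis". The ranking that defines severity is "simple without atypia hyperplasia < simple with atypia hyperplasia < complex without atypia hyperplasia < complex with atypia hyperplasia". It sorts by architecture first and by atypia second, and no reason is given.

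The selected diagnosis feeds the by-visit summary, listed in SAP Appendix B (7.2) as "Table 14.4.12.2 Endometrial Biopsy Diagnosis by Classification and Primary Diagnosis up to Month 6 Follow-up". The possible results for that summary keep the four subtypes apart: "Hyperplasia: Simple with Atypia, Simple without Atypia, Complex with Atypia, Complex without Atypia". No row counts atypia on any reading.

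The documents differ on how many readings there are. For hyperplasia or malignancy the SAP says that "a second read should be done at other visit than screening". Protocol 10.4.5 says: "Endometrial biopsies of hyperplasia of any type will be submitted for assessment by three independent expert pathologists". It adds that these pathologists are blinded to treatment and to one another.

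**The concern.** The purpose of taking the most severe of several readings is to keep the table from understating what was seen. Here the rule can understate one feature. If one pathologist records simple hyperplasia with atypia and another records complex hyperplasia without atypia, the table shows only the second.

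Pathological change in the endometrium is a listed safety endpoint in both documents. One arm receives estradiol and norethisterone acetate with linzagolix. After early termination the SAP reports efficacy in listings only, so the safety tables carry the report. With few subjects randomized, one case can change how a subtype row reads. Atypia is also a feature that the SAP chose to tabulate separately.

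**Working it through.** The plan states no figure to reproduce. The check applies the SAP rule to every possible set of readings.

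**Inputs.** The ranking and the selection rule come from SAP 4.8.9.1. The number of readings is two (the SAP's second read) or three (the pathologists in Protocol 10.4.5). Every reading is assumed to be one of the four hyperplasia subtypes. Write S for simple, C for complex, + for with atypia and − for without. The SAP order is then S− < S+ < C− < C+.

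**Two readers, discordant pairs.** Four subtypes give 4 × 3 / 2 = 6 unordered pairs.

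| Readings | Selected | Atypia read? | Atypia in table? |
|---|---|---|---|
| S−, S+ | S+ | yes | yes |
| S−, C− | C− | no | no |
| S−, C+ | C+ | yes | yes |
| S+, C− | C− | yes | **no** |
| S+, C+ | C+ | yes | yes |
| C−, C+ | C+ | yes | yes |

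One pair in six loses the atypia reading. Readers disagree about atypia itself in four of the pairs, so the loss is one of those four.

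**General count for k readers.** The loss occurs exactly when no reading is C+, at least one is S+ and at least one is C−. The number of ordered combinations is 3^k − 2 × 2^k + 1, out of 4^k. Combinations with any atypia reading number 4^k − 2^k.

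- k = 2: 9 − 8 + 1 = 2 of 16, or 2 of the 16 − 4 = 12 with any atypia reading.
- k = 3: 27 − 16 + 1 = 12 of 64, or 12 of the 64 − 8 = 56 with any atypia reading.

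The 12 for three readers are the orderings of {S−, S+, C−} (6), {S+, S+, C−} (3) and {S+, C−, C−} (3). In the middle group two of three readers recorded atypia, so a majority finding can also be lost: 3 of the 12.

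**Reversing the priority.** With the order S− < C− < S+ < C+, no combination loses atypia (0 of 16 and 0 of 64). A reading of complex architecture is then lost in the same cases: 2 of 16 and 12 of 64. The SAP order loses complex architecture in none. Any single ranking of the four labels must give up one feature for the pair S+ and C−.

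**Does anything in the SAP put the reading back into the table?** The section says that "a subject could be in several diagnoses (e.g. if for example diagnoses 2 and 3 are fulfilled". This concerns diagnosis fields 2, 3 and 4; it does not say that a reading not selected is added back. The end of the section sends all readings to listings, which is a different output.

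**The case against.** Four arguments limit the point, and most of each stands.

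- **Nothing leaves the report.** A reader might infer that the atypia finding is deleted. It is not. SAP 4.8.9.1 puts multiple readings in the listings (Listing 16.2.9.11), and the subject still counts as hyperplasia under primary diagnosis 1. In a small trial such a case could be found by eye. What remains is that the table itself would show no atypia for that subject.
- **The SAP does not contradict its own criterion.** A reader might infer a conflict from the prior-biopsy waiver in the same section, which accepts an earlier biopsy "which shows no endometrial atypical hyperplasia or adenocarcinoma". That sentence governs when a screening biopsy may be skipped; it is not a severity scale. It also differs from the waiver in Protocol 10.2.1 and 10.4.5, which refers to hyperplasia of any type. Elsewhere the line is drawn at any hyperplasia: the discontinuation rules in Protocol 10.7.2.1 and SAP 2.3.1, and the expert review in Protocol 10.4.5. The waiver is therefore weak evidence about how readings should be ranked.
- **The documents cannot settle the right order.** They cite no pathology classification, so they do not support a claim that atypia must rank first. An atypia-first order would only move the loss to complex architecture.
- **The affected number may be zero.** Enrolment stopped well short of target. A Month 6 biopsy is required only above 5 mm endometrial thickness, and further readings follow only hyperplasia or malignancy. The same order applies to every arm, and no formal test of the biopsy results is specified.

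None of this restores to Table 14.4.12.2 a feature that the SAP tabulates and a blinded reader recorded.

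**Conclusion.** The point holds as a minor reporting gap. When at least one reading is simple with atypia, at least one is complex without atypia and none is complex with atypia, the subtype rows of Table 14.4.12.2 show no atypia for that sample. That is 1 of 6 discordant pairs for two readers and 12 of 64 ordered combinations for three. These shares describe the rule and should not be read as expected frequencies.

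The conclusion rests on two assumptions: that the selected reading alone fills the subtype rows, as the SAP text implies, and that no row for any reader is planned, as the table list indicates. The hyperplasia count and the listings are unaffected. Discontinuation is also unaffected, because hyperplasia of any type triggers it.

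**What to change.** 1. Add a row to Table 14.4.12.2, by visit and treatment group, for subjects with atypia on any reading. Add a matching row for complex architecture on any reading. Together they keep both features whichever order is used.
2. State the basis for the severity order in SAP 4.8.9.1, or revise it with the study pathologists.
3. Reconcile the SAP's second read with the three pathologists in Protocol 10.4.5, because the number of readings determines how often the rule can operate.
4. Reconcile the waiver wording: the SAP names atypical hyperplasia, the protocol names hyperplasia of any type.

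The cost is a few lines of SAP text and one or two table rows from data already collected and listed. If the rows are added after unblinding, label them post hoc.

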**10.2.3.4 Study visit: Month 6 FU – End of Follow-up visit**

Month 6 FU visit should be scheduled on Day  $337 \pm 7$  days after Day 1 (or  $168$  days  $\pm 7$  days after last IMP intake for early discontinued subjects).

The following evaluations and tests will be performed at Month 6 FU Visit:

- ePRO and ClinRO completion, ideally before any other procedures or assessments: EHP-30, HRPQ, HRUQ, PROMIS, EQ-5D-5L, mPGIS, PPGIC completion (mPGIS and PPGIC must be completed last)
- Collection and deactivation of eDiary
- Concomitant treatments recording
- AE recording
- Completion of the paper C-SSRS questionnaire version “since last study visit” (see Appendix T) for patients for whom the C-SSRS was completed at the previous study visit.
- ECG
- Physical examination, including weight recording
- Urine pregnancy test
- TVUS of uterus
- Endometrial biopsy if no endometrial biopsy was obtained at Month 6 nor at any visit since Month 6 (see section 10.4.5). If no tissue is available, the biopsy should be repeated as soon as possible in the following days.
- BMD assessed by DXA for femoral neck, hip and spine. This DXA can be performed  $\pm$  10 days from the Month 6 FU study visit.

This visit constitutes the end of study participation except for subjects with a BMD decrease from baseline  $> 1.5\%$  for lumbar spine and/or  $> 2.5\%$  for total hip who should have a repeat DXA scan 6 months later for a BMD follow-up assessment.

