The efficacy variables planned in the protocol will not be analyzed due to the early study termination and the low number of subjects randomized.

2.5.2. **Pharmacokinetic Variables**

The pharmacokinetic variables planned in the protocol will not be analyzed due to the early study termination and the low number of subjects randomized.

2.5.3. **Safety Variables**

Safety endpoints include:

- Change from baseline to each scheduled assessment in BMD measured by DXA of lumbar spine (L1-L4), femoral neck, and total hip
- Incidence and severity of treatment emergent adverse events (TEAEs)
- Incidence and severity of hypoestrogenic TEAEs (hot flush)
- Time to the first post-treatment menses
- Changes in clinical laboratory assessments (hematology, biochemistry, coagulation parameters, hormones, lipids and urinalysis) from baseline to each scheduled assessment
- Any pathological changes from baseline in the endometrium as assessed by histology from endometrial biopsies
- Changes from baseline to each scheduled assessment in any other safety parameter including weight, vital signs, ECG, gynecological assessments and endometrial thickness

Safety analyses are described in Section 4.8.

Note that the endpoint “Time to the first post-treatment menses” was initially planned in the protocol, but will not be described in this SAP, because the study was stopped prematurely, and all subjects couldn’t be followed to evaluate this endpoint.

2.5.4. **Exploratory Variables**

The exploratory variables planned in the protocol will not be analyzed due to the early study termination and the low number of subjects randomized.

Sponsor:	ObsEva		
Protocol:	18-OBE2109-002		
Document Version No.:	1.0	Document Date:	18-MAY-2021

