For other safety results, data from early discontinuation should be compared to theoretical visits dates. Only assessments within the window of theoretical date +/-14 days will be used for analyses, if it is planned to have a such assessment at this visit and no other assessment is in the window. If a subject discontinued in the main treatment period, date will be compared to the theoretical visit dates in main treatment period as described in Table 3. If a subject discontinued in the follow-up period, date will be compared to the theoretical visit dates in Follow-up period from

Sponsor:	ObsEva		
Protocol:	18-OBE2109-002		
Document Version No.:	1.0	Document Date:	18-MAY-2021

Table 4.

For unscheduled safety assessments, if the assessment occurs in a window of +/- 14 days of a planned eCRF visit for which it was planned per protocol to have such assessment, and no assessment was done for that visit, the assessment will be assigned to that visit. If the assessment is equally distant from two eCRF visits with no corresponding safety assessment, the assessment will be assigned to the next visit.

For biopsy, DXA assessment or laboratory assessment, if an assessment has been assigned in external data to a follow-up visit of the main study for subjects entered extension study, the visit of assessment should be reassigned with the same rules described above for unscheduled safety assessment.

Table 3 Theoretical Visit Dates in Main Treatment Period

Visit	Theoretical Date
Month 1	Day 29
Month 2	Day 57
Month 3	Day 85
Month 4	Day 113
Month 5	Day 141
Month 6	Day 169

Sponsor:	ObsEva		
Protocol:	18-OBE2109-002		
Document Version No.:	1.0	Document Date:	18-MAY-2021

Table 4 Theoretical Visit Dates in Follow-up

Visit	Theoretical Date
Month 1 FU	Month 6 date or treatment discontinuation date + 28
Month 2 FU	Month 6 date or treatment discontinuation date + 56
Month 3 FU	Month 6 date or treatment discontinuation date + 84
Month 4 FU	Month 6 date or treatment discontinuation date + 112
Month 5 FU	Month 6 date or treatment discontinuation date + 140
Month 6 FU	Month 6 date or treatment discontinuation date + 168

4.2.11. **Baseline Definition**

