5. CHANGES TO PLANNED ANALYSES

Following the early termination of the study and due to the number of subjects randomized being really less than the target number if the study had been fully enrolled, the analyses planned in the protocol on efficacy and pharmacokinetic assessments have been removed and only listings for these assessments will be displayed. The statistical analysis plan (SAP) will be focused on the safety analysis and all safety.

For safety endpoints, the endpoint “Time to the first post-treatment menses” was initially planned in the protocol, but will not be described in this SAP, because the study was stopped prematurely and all subjects couldn’t be followed to evaluate this endpoint.

Sponsor:	ObsEva		
Protocol:	18-OBE2109-002		
Document Version No.:	1.0	Document Date:	18-MAY-2021

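### No table counts the women with endometrial pathology after baseline: biopsies are summarized only by visit, and some fall outside every visit row

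*SAP*

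**What the plan says.** SAP 2.5.3 lists among the safety endpoints "Any pathological changes from baseline in the endometrium as assessed by histology from endometrial biopsies". SAP section 5 removes one safety endpoint, time to first post-treatment menses, which "was initially planned in the protocol, but will not be described in this SAP". The histology endpoint is not removed, and SAP 1.2 names endometrial health among the safety objectives.

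SAP 4.8.9.1 plans two summaries and a listing. The first is by time point: "A summary at each time point will be performed (number and percentage of subjects with normal, abnormal, not assessable". The second is by diagnosis: "Biopsy assessment will be summarized by classification (primary diagnosis 1) and primary diagnoses (diagnoses 2, 3 and 4) at each visit". A most-severe rule exists, but only across several readings of one sample. A rule for choosing among several biopsies exists for screening only. The table list in SAP 7.2 has Tables 14.4.12.1 and 14.4.12.2 for biopsies, and neither title mentions a shift or a worst result after baseline.

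The timing of the biopsy varies between women. SAP 4.8.9.1 asks for "One at Month 6 if endometrial thickness in TVUS is > 5 mm" and then "One at Month 1 FU, 2 FU, 3 FU, 4 FU, 5 FU or 6 FU if not obtained at Month 6", or again if the preceding diagnosis was not benign.

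SAP 4.2.10 decides which off-schedule safety assessments reach the tables. An early-discontinuation assessment is used only within 14 days of the theoretical date of a visit at which that assessment is planned. An unscheduled one is placed at a planned visit within 14 days if one was planned there "and no assessment was done for that visit, the assessment will be assigned to that visit".

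**The concern.** The endpoint concerns a woman: did her endometrium become pathological after she started treatment, compared with screening? The planned tables describe visits. Where samples come on different dates for different women, and where some women are sampled again because of an earlier result, visit rows hold different and partly overlapping groups. Their percentages cannot be read as incidence, and they cannot safely be added.

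A second gap points the same way. A biopsy that matches no planned visit enters no row. Such biopsies come from women who stopped early or bled suspiciously, which are the women in whom an endometrial finding matters most.

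What is at stake is a plain statement, by arm, of how many women had hyperplasia or malignancy after first dose, and out of how many assessed.

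**Working it through.** The plan states no figure on this point, so there is none to reproduce. The check has four steps.

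**1. Where a scheduled biopsy after baseline can fall.** For women who enter main-study follow-up: Month 6 plus Month 1 FU to Month 6 FU, so 1 + 6 = 7 visits across such women. Extension entrants have only Month 6 in this study. Women who stop before Month 3 do not enter follow-up (Protocol 8 and 10.7.2).

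**2. Do the visit tables determine the number of women affected?** Take three women and two possible data sets. A dash means no biopsy.

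| Data set | Woman | Month 6 | Month 1 FU |
|---|---|---|---|
| X | 1 | not benign | not benign |
| X | 2 | benign | – |
| X | 3 | – | benign |
| Y | 1 | not benign | benign |
| Y | 2 | benign | – |
| Y | 3 | – | not benign |

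Both give Month 6: 1/2 and Month 1 FU: 1/2. The count of women ever affected is 1/3 in X and 2/3 in Y. The tables therefore do not determine it once a non-benign result has been followed by a repeat.

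**3. Even with one biopsy per woman, the visit percentage is not the per-woman rate.** Assumptions, since the documents give neither number: 15, 30 or 50 women per arm biopsied once after baseline, 40% to 70% of them at Month 6, one hyperplasia found at Month 6, and a visit row that uses the women biopsied at that visit as denominator.

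| Women biopsied | Per-woman rate | Month 6 row, 70% sampled then | Month 6 row, 40% sampled then |
|---|---|---|---|
| 15 | 1/15 = 6.7% | 1/10 = 10.0% | 1/6 = 16.7% |
| 30 | 1/30 = 3.3% | 1/21 = 4.8% | 1/12 = 8.3% |
| 50 | 1/50 = 2.0% | 1/35 = 2.9% | 1/20 = 5.0% |

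**4. Which biopsies enter no row.** Women who stop between Month 3 and Month 6 undergo the Month 6 procedures (Protocol 10.7.2), which include a biopsy unless the endometrium is 5 mm or thinner. SAP 4.2.10 compares their dates with the treatment-period visits in SAP Table 3. Biopsy is planned at only one of those, Month 6, Day 169. The window is 169 − 14 = Day 155 to 169 + 14 = Day 183. A withdrawal biopsy from Day 85 to Day 154 falls outside it. That is 154 − 85 + 1 = 70 of the 84 days from Day 85 to Day 168. This is a share of calendar days, not of withdrawals. A for-cause biopsy for heavy or suspicious bleeding (Protocol 10.4.5), taken more than 14 days before the Month 6 visit, has no planned biopsy visit near it either. Both kinds appear only in Listing 16.2.9.11.

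**Comparison within the SAP.** Per-woman or change-from-baseline summaries are specified elsewhere: shifts for physical examination (4.8.5), worst on-treatment value for liver tests and progesterone above a limit at least once (4.8.4), and emergence at any time after baseline for the suicidality scale (4.8.10). Biopsy, whose timing varies most between women, has none.

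**The case against.** The strongest reply is that the information will exist. Listing 16.2.9.11 shows every biopsy, and enrolment stopped well short of target, so rare findings can be counted by hand. Clinically significant abnormal findings are also to be reported as adverse events (Protocol 12.1.2), and the adverse event tables count a woman once per term. This stands in part. A reader might infer that the report cannot state how many women were affected, and the documents do not support that. But the adverse event tables are split by period and depend on investigator judgement, and a hand count has no prespecified rule for repeats, windows or denominator.

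The SAP also says that a subject is counted once for classification. That sentence follows directly on the by-visit sentence and reads as a rule within a visit. Read across visits, it would still need a rule for which biopsy counts.

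The re-biopsy rule is contested inside the documents. SAP 4.8.9.1 and Protocol 10.2.3.1 to 10.2.3.3 repeat the biopsy after any non-benign result; Protocol 10.4.5 excepts malignancy and hyperplasia. These passages must be reconciled. A reader might picture one hyperplasia case recurring at visit after visit, or filling up to seven rows. The documents do not support that as settled design, because of 10.4.5 and because Protocol 10.2.3.4 calls for a biopsy at Month 6 FU only when none was obtained at or since Month 6. Where 10.4.5 was followed, step 2 reaches only other non-benign results; steps 3 and 4 are unaffected.

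Hyperplasia on the screening biopsy is given as a ground for exclusion (Protocol 9.2.2, criterion 20), so a shift table adds little beyond the worst result. That is fair. It still identifies women randomized without a screening biopsy, which Protocol 10.4.5 allows.

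**Conclusion.** The endpoint is retained, and no planned table computes it. The visit rows do not fix the number of women per arm with pathology after baseline, and the ±14-day rule keeps some relevant biopsies out of all rows. The size in the actual report is unknown, because the documents give no biopsy results and no number randomized. The ranges in step 3 rest on the assumptions stated there. Step 4 assumes that a withdrawal biopsy is handled as an early-discontinuation assessment and not entered in the eCRF under a scheduled visit.

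Two wider readings are not supported. One is that every woman's biopsy can fall at any of seven visits; this applies only to those who enter main-study follow-up. The other is that a failed sample blocks its own repeat. Protocol 10.2.3.4 says for Month 6 FU "If no tissue is available, the biopsy should be repeated as soon as possible in the following days", and the SAP does not say whether a no-tissue attempt counts as an assessment done or whether the repeat counts as unscheduled. That is an ambiguity to close, not a demonstrated loss of data.

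This is a gap in a descriptive safety summary of a trial that ended early. It affects no hypothesis test, and it is worth repairing because the repair is small.

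**What to change.** Add one per-woman block by arm to Table 14.4.12.2:

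- **Result:** worst assessable diagnosis from any biopsy after first dose up to the end of main-study participation (scheduled, repeat, withdrawal or for-cause), regardless of visit window, set against the screening classification. State that the Month 6 biopsy counts for extension entrants, because the end-of-study date in SAP 4.2.12 stops before Month 6 for them.
- **Denominator:** women with at least one assessable biopsy after first dose.
- **Shown separately:** women with no assessable biopsy after first dose, and women with no screening biopsy.
- **Timing:** split or flag on-treatment and Month 6 samples versus follow-up samples.

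Add one sentence to SAP 4.8.9.1: an assessable repeat replaces a no-tissue sample at the same visit. Reconcile the re-biopsy rule between Protocol 10.4.5 on one side and Protocol 10.2.3.1 to 10.2.3.3 and SAP 4.8.9.1 on the other, and state in the report which rule was followed.

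The cost is one descriptive block and one sentence, with no new procedures or data. The downside is that the block pools samples taken at different times since last dose; the timing split limits this.
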